5.4 Informed Consent Procedures/Enrollment

5.3a. Aim 1 Vaccine Acceptance Trial. This is a cluster randomized controlled trial design and thus randomization is at the level of VAMC within VISNs 16 and. During the pre-implementation phase (Exempt protocol #E21-06), the study team will meet with leadership of VISNs 16 and 21

and their respective VAMCs to describe the study aims, methods and requirements of each study arm as well as the potential risks/burden and benefits of participation. Specifically, at these meetings, the study team will explain that there is a 50/50 chance that a VAMC will be randomized to be an Intervention or Usual Care site and what is required of each condition. A VAMC assigned to Usual Care will have no specific trial intervention requirements beyond their usual level of participation in national and local initiatives to improve COVID-19 vaccine acceptance. At both Intervention and Usual Care sites, the study team will perform quarterly "environmental scans". The environmental scan survey will include questions about site specific barriers to COVID-19 vaccination, current programs/initiatives in the clinic or local community that are improving or have had no impact on vaccination rates, and the perceived importance that the VAMC/CBOC and clinic staff is placing on vaccination (**Environmental Scan Survey, in preparation**). At Usual Care sites, a point of contact will be chosen from each clinic and CBOC to complete the environmental scan, and at Intervention sites, the Site Champion (**see below**) will perform the quarterly scan.

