This is a cluster randomized parallel group trial design in which the unit of randomization will be at the level of VAMC facility. Cluster randomization is often used to avoid contamination between those receiving the intervention and those who are not. In this case, the Vaccine Acceptance Intervention will occur at Intervention sites and not at Usual Care sites, but we will monitor for evidence of contamination, and if not able to fully guard against it (VA is a national system), we will document examples of potential contamination in the environmental scans described previously.

Randomization will be stratified by VISN (either 16 or 21) and covariate constrained by baseline primary series vaccination rates.⁸¹ Given the likely relatively small number of VAMCs that will be randomized (N \leq 16), we are selecting only one stratification variable (VISN or geographic location) and one or more covariates to constrain on. We have chosen to stratify on VISN given the central importance of location on vaccination outcomes and so as not to have all VAMCs in one VISN randomly assigned to the same study arm. We will also constrain on baseline primary series vaccination rates according to whether sites have lower or higher rates at the start of the study. The number of sites that participate will guide the feasibility of constraining on additional factors, such as rurality, because current data (see **Appendix**, Table 1) suggests that rurality is an important determinant of whether individual patients accept COVID-19 vaccination.

Blinding

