The study PIs and co-investigators, other research staff (except for the study statistician, see below), qualitative interviewers and participating VA staff will be unblinded because they are involved in delivering the intervention or, in the case of the qualitative researchers, will be tasked with interviewing study stakeholders about the intervention or implementation strategies. In contrast, the study evaluators, study statistician, and Veterans at VAMC sites in VISN 16 and 21 will be blinded to study arm assignment (Vaccine Acceptance Intervention vs. Usual Care). Thus, evaluators will conduct the study survey in 450 Veterans, and while they will be aware of COVID-19 vaccination status, they will not be apprised of study arm. In addition, unless Veterans are unintentionally informed, Veterans will not know to which arm their VAMC has been randomized. Blinding of the study statistician conducting the outcomes analyses, survey evaluators, and the Veteran participants is important to protect the internal validity of study findings. Despite this being a cluster RCT, outcomes will be ascertained at the patient level.

5.3.b. Aim 2 Veteran Surveys and Interviews

Additional Recruitment Methods: The VA Corporate Data Warehouse (CDW) will be used (via a HIPAA waiver for recruitment) to identify over 8,000 eligible patients over the course of 18 months for inclusion in the cross-sectional survey and qualitative interview across all participating VAMC clinics in VISNs 16 and 21. The following are the broad eligibility criteria used to search VA administrative databases for potentially eligible participants:

- ≥1 visit(s) at a participating VISN 16 or 21 inpatient or outpatient service after the start of the trial at their site.
- Are members of one of two groups with respect to COVID-19 vaccination status:
 - (1) You have either not started COVID-19 vaccination, (2) you received your most current dose of the primary series of a COVID-19 vaccine series after clinicians at your site received the training intervention and within the past 150 days.
- No evidence of dementia using ICD-10 diagnostic codes.

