5.4 Inclusion/Exclusion Criteria (All Study Aims)

Each study Aim has a unique set of inclusion and exclusion criteria summarized below.

5.4. a. Aim 1: Cluster RCT of Vaccine Acceptance Intervention (Randomization at the level of VAMC)

Inclusion criteria:

o Primary care clinic visit in VISN 16 or 21

Exclusion criteria:

o Per VISN or VAMC leadership, the clinic or CBOC has extreme staffing shortages such that it would not be feasible or in the best interests of patient care to allow clinic or CBOC staff release time to participate in trainings or other meetings related to the trial.

5.4.b. Aim 2: Evaluation of recently vaccinated (N=360) and unvaccinated (N=90) Veterans across VISNs 16 and 21 at Intervention and Usual Care sites. *Inclusion criteria:*

- ≥1 visit(s) at a participating VISN 16 or 21 inpatient or outpatient clinic after the start of the trial at their site, and
- At the time of recruitment, COVID-19 vaccination status is verified as one of the following: (1) has not initiated COVID-19 vaccination; (2) has received the most current dose of the primary series of a COVID-19 vaccine after clinicians at their site received the training intervention and within the past 150 days.

Exclusion criteria:

- No consistent ability to be contacted by phone
- Evidence of dementia using ICD-10 diagnostic codes.

5.4.c. Aim 3: Implementation-focused Interviews with VISN 16 and 21 Staff and HCPs

Inclusion criteria: Staff and HCPs work at one of the clinics involved in the study

Exclusion criteria: Staff or HCPs declines invitation to participate in the interview.

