5.6.a Training Health Behavior Coordinators in Vaccine Acceptance. One of this study's operational partners, the VA National Center for Health Promotion and Disease Prevention (NCP) supports MI training of PACT staff throughout VA through a "train-the-trainer model." First, NCP provides in-depth training for all Health Behavior Coordinators (HBCs) that includes content on MI and other patient-centered communication skills, as well as strategies to lead an engaging MI training With PACT staff. Once HBCs have participated in the training, they are then tasked with training PACT staff at their local facility in MI and other patient-centered communication skills. HBCs have trained thousands of PACT providers across the VA health care system in the use of MI and other communication techniques.

During the first 3 months of the study, [name] (Study mPI and SFVAHCS Health Behavior Coordinator) will collaborate with [name] (co-I; CAVHS Health Behavior Coordinator) and [name] (co-I; SFVAHCS Health Behavior Coordinator) to train HBCs based at VAMCs randomized to the VAI condition in VISNs 16 and 21. HBCs will be trained in the Vaccine Acceptance Intervention, which will rely heavily on MI techniques and will also include discussions of vaccine hesitancy and risk communication. The training will closely align with NCP's two-hour MI training for PACT staff so the structure will be familiar to HBCs but will differ from NCP's MI training in that all content will be focused on COVID-19 vaccine acceptance. The estimated time to train HBCs will be approximately 4 hours. The training will review MI training strategies, information regarding COVID-19 vaccines, risk communication and vaccine hesitancy. Following the training, HBCs at intervention sites will be invited to attend a twice-monthly consultation call, to discuss recent advances regarding MI and COVID-vaccine acceptance, to review training strategies and problem-solve any training or intervention issues that may arise.

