1. STUDY SYNOPSIS

Title	The COVID-19 Vaccine Acceptance Study (CoVAcS)		
	The design is a hybrid type 2 (implementation-effectiveness) study. It		
Study Design	consists of a pragmatic cluster randomized controlled 2-arm superiority trial		
	with unit of randomization Veteran Healthcare System (VAHCS) (Aim 1); a		
	survey (Aim 2) and qualitative interviews using purposive sampling (Aim 3).		
Study Duration	3 years		
Trial Sites	VISN 21 and VISN 16 VA facilities		
	Conduct a one-year pragmatic cluster randomized trial to determine the		
	effectiveness of a vaccine acceptance intervention (VAI) training for		
Objectives	healthcare providers and staff in increasing the uptake of any COVID-19		
	vaccination dose in Veterans; conduct a survey to identify predictors of		
	vaccine acceptance/hesitation.		
Number of	10 trial sites in VISNs 16 and 21 (including approximately 90,000 -100,000		
Participants	(Expected); 338,000 (Actual) Veterans		
- articipants	Survey completed: 450 (Expected) Veterans; 224 (Actual) Veterans.		
	Belonging to either VISNs 16 or 21:		
	Aim 1 Trial: Veterans included in the analysis have had one or more primary		
	care visit(s) at a participating VA facility within the past year at the start of		
	site-level randomization.		
Main Inclusion Criteria			
	Aim 2 Survey: Veterans eligible for the trial and who (1) had not started the		
	COVID-19 vaccination and (2) received their most current dose of the		
	primary COVID-19 series in the prior 150 days from when they were		
	contacted and without ICD-10 diagnostic codes indicating dementia and		
	have received primary care at their study site since the study start date at their site.		
	VAI training for health care providers and staff, which includes the use of		
Intervention	Motivational Interviewing to promote vaccine acceptance.		
Duration of	Motivational interviewing to promote vaccine acceptance.		
Intervention and	Intervention (Provider VAI training): 12 months; Follow-up 12-months.		
Follow-up	intervention (Frovider var training). 12 months, ronow-up 12-months.		
·	Study statistician, study evaluators, and Veterans will be blinded to study		
Blinding	arm.		
	Aim 1: Receipt of at least one dose of the COVID-19 vaccine.		
Primary Outcome	74111 1. Necespt of at least one dose of the covid 15 vaccine.		
	All analyses will be according to intent to treat. The difference in proportion		
Primary Analysis	of Veterans receiving any dose at 12 months will be compared between		

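### Read literally, the protocol's Aim 2 rule for recently vaccinated respondents admits no usual-care Veteran, and the SAP states a different rule

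*Protocol*

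**What the plan says.** Protocol 5.4.b heads its Aim 2 criteria as covering "Veterans across VISNs 16 and 21 at Intervention and Usual Care sites". It then defines two groups: Veterans who have not started COVID-19 vaccination, and recently vaccinated Veterans. A member of the second group must be someone who "has received the most current dose of the primary series of a COVID-19 vaccine after clinicians at their site received the training intervention" and whose dose falls in the last 150 days. The database search criteria in Protocol 5.3.b use the same anchor: "after clinicians at your site received the training intervention and within the past 150 days".

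On where training takes place, the Randomization text in the protocol says "the Vaccine Acceptance Intervention will occur at Intervention sites and not at Usual Care sites". Protocol 5.3a adds: "A VAMC assigned to Usual Care will have no specific trial intervention requirements". Protocol 5.6.a plans "to train HBCs based at VAMCs randomized to the VAI condition in VISNs 16 and 21", and those coordinators train the primary care staff at their own facility.

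The SAP synopsis (section 1, Main Inclusion Criteria) places the dose of the "primary COVID-19 series in the prior 150 days from when they were" contacted. It also requires primary care at the study site since that site's start date. It does not mention training.

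**The concern.** The dose condition depends on an event that occurs in one arm only. A rule of this kind cannot select comparable vaccinated respondents from both arms.

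Aim 2 needs vaccinated respondents from both. Protocol 3.0 asks whether Veterans at intervention sites report more vaccination discussions than those at usual-care sites, and whether decision factors and pandemic impacts differ between the two. Protocol 3.0 and 5.3 spread the sample equally across facilities, and the Aim 2 analytic plan in 5.9 draws the interviews equally from both arms. Oversampling of vaccinated Veterans is justified as a way to describe the intervention's impact on the decision to accept vaccination.

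If the rule were applied as written, every usual-care respondent would be unvaccinated. A between-arm contrast among the vaccinated would have no comparator. The vaccinated-versus-unvaccinated model in SAP 9.2.1 would also set vaccinated Veterans from intervention sites only against unvaccinated Veterans from both arms.

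**Working it through.** **1. The plan's own sample.** Protocol Table 3: 8,037 × 0.35 = 2,813; × 0.80 = 2,250; × 0.20 = 450. By month: 25 × 18 = 450, made up of 20 × 18 = 360 vaccinated and 5 × 18 = 90 unvaccinated. These figures reproduce.

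**2. The rule applied to each arm.**
- Intervention site, vaccinated: a training date exists, so the condition can be met.
- Usual-care site, vaccinated: no training takes place and no substitute date is defined, so the condition cannot be met.
- Either arm, unvaccinated: the training condition does not apply, so both arms qualify.

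**3. Size if applied literally.** SAP 6.1.1.2 gives 5 sites per arm.
- Equal split across sites: 360 × 5/10 = 180 planned vaccinated respondents are ineligible.
- Split by arm population (190,427 of 338,718 in usual care, 56.2%): 360 × 0.562 ≈ 202 are ineligible.
- Equal split with no replacement: usual care holds 0 vaccinated and 90/2 = 45 unvaccinated; intervention holds 180 and 45.

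**4. Protocol against SAP.** Both use a 150-day look-back, and both attach the site start date to the visit. Only the protocol adds the training condition to the dose. A vaccinated usual-care Veteran dosed 100 days before contact, with a primary care visit since site start, passes the SAP's dose and visit conditions but not the protocol's.

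**5. Dose windows under a hypothetical workaround.** Suppose usual-care sites used the 150-day limit alone while intervention sites also applied the training condition. Neither document describes this. Training dates are not given, so I assume training 0, 90 or 180 days after site initiation. Inputs: initiation dates from 14 February to 20 April 2022 (SAP Table 2, all ten sites, because arm is not shown there) and survey dates 25 May 2022 to 7 August 2023 (SAP 8.2.1), which is 440 days.

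On the first survey day the 150-day look-back reaches 26 December 2021, before any site's initiation. Days on which the training condition shortens the intervention window = (initiation + lag + 150 days) − 25 May 2022:

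| Assumed lag | Days affected, of 440 | Share | Intervention window on first survey day (usual care: 150 days) |
|---|---|---|---|
| 0 days | 50–115 | 11–26% | 35–100 days |
| 90 days | 140–205 | 32–47% | 0–10 days |
| 180 days | 230–295 | 52–67% | 0 days |

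From 150 days after training the two windows are identical.

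**The case against.** The strongest reply is that this is loose drafting. The heading of 5.4.b names usual-care sites and the sampling plan requires them, so staff presumably applied some workable rule. The survey closed on 7 August 2023 and protocol version 5.0 is dated 15 December 2023, so new wording changes no recruitment and could misdescribe how respondents were selected. Aim 2 is described as primarily descriptive, and SAP 9.2.1 plans a comparison of vaccinated with unvaccinated respondents, with no intervention-versus-usual-care model.

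Much of this stands. It limits the consequence and means that any rewording must come with a statement of what was done. It does not remove the contradiction: the condition appears twice in the current protocol, cannot be met in one arm, and differs from the SAP.

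Three stronger readings are tempting and are not supported:
- A reader might infer that none of the 139 vaccinated respondents came from usual care. SAP 6.2.1.2 gives no split by arm, and no document says which rule was used.
- A reader might infer that the arms had different dose windows, perhaps by about three months. That needs the undocumented workaround and an assumed training date. The three months in Protocol 5.6.a concern training the coordinators; the SAP synopsis lists provider training as 12 months.
- A reader might infer that the SAP requires the dose to follow site start. It ties the start date to the primary care visit.

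**Conclusion.** The point holds as an internal contradiction in the protocol and a conflict between protocol and SAP. The rule as written makes vaccinated usual-care Veterans ineligible: about 180 of the 360 planned under an equal split, or about 202 if split by arm population. Whether anyone was in fact excluded is unknown.

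The effect is confined to the vaccinated group in Aim 2, and severity is low. Any difference in dose windows is conditional on the assumptions in the working and is not a finding about the data.

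**What to change.** - **Wording.** Remove the training condition and state one arm-neutral rule identically in Protocol 5.3.b, Protocol 5.4.b and SAP section 1. The SAP rule serves: dose within 150 days before contact, and visit since site start.
- **Record of what was done.** State which dose rule was actually used in recruitment at intervention sites and at usual-care sites, so that the revised text does not misdescribe selection.
- **Reporting.** Give vaccinated and unvaccinated respondents by arm. If usual care has few or no vaccinated respondents, draw no intervention-versus-usual-care conclusions among the vaccinated.
- **Sensitivity analysis.** Restrict any intervention-versus-usual-care comparison to respondents dosed on or after their site's initiation date in SAP Table 2. This is an added condition that is in neither document and should be labelled as such.

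The cost is a text change, a tabulation and a date filter on data already collected. A few of the 224 surveys would drop from the sensitivity analysis; the number depends on dose dates that the documents do not give. The filter cannot recover usual-care Veterans who were never recruited; only the counts by arm would show whether that happened.

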5.5 Additional Study Methods

5.5.a. Vaccine Acceptance Trial Overview (Aim 1). We will conduct a one-year cluster randomized parallel group trial stratified by VISN using covariate constrained randomization (e.g., baseline vaccination rates, rural/urban clinics, facility size).⁸¹ Specifically, we will compare a Usual Care (UC) versus Vaccine Acceptance Intervention (VAI) with randomization at the level of VA Medical Center (VAMC).⁸¹ In collaboration with our VA operations partners, NCP, OPCC-CT and the Office of Health Equity, VISNs 16 and 21, and the CDC Vaccine Confidence Team, we will use these conceptual frameworks-Vaccine Hesitancy and Motivation, Risk Communication, and i-PARiHS, supported by MI-informed communication, to iteratively refine, tailor, implement, facilitate and test an intervention to improve COVID-19 vaccination acceptance in Veterans across culturally and geographically diverse regions (Northern and Central California, Nevada, Hawaii, Arkansas, Louisiana, Mississippi and Texas).

5.5.a.1. Usual Care (UC) Condition: Usual Care will consist of all national and local initiatives to promote COVID-19 vaccine acceptance in Veterans such as mobile clinics, outreach calls, public service announcements targeted at Veterans, lotteries, etc. Usual Care initiatives will be documented and described in detail through quarterly environmental scans at all study sites.

Figure 2. Vaccine Acceptance Intervention

5.5.a.2. Vaccine Acceptance Intervention (VAI):

The VAI condition will use the evidence-informed conceptual frameworks,^{19,85-88,90} Vaccine Hesitancy and Motivation, Risk Communication, Motivational Interviewing (MI) strategies, and the Integrated Promoting Action on Research Implementation in Health Services (i- PARiHS) to improve COVID-19 vaccination rates among Veterans. As described in Figure 2, the VAI intervention utilizes a multi-pronged approach to increase Veteran vaccine acceptance. First, the research team will train Health Behavior Coordinators (HBCs) at intervention sites in VAI. HBCs will then train PACT teams at their site and Whole Health Coaches, Peer Specialists and other VA staff in VAI strategies to use with Veterans. Whole Health Coaches, Peer Specialists and other VA Staff will conduct outreach calls, using VAI strategies, with Veterans.

Figure 3. Three C's Model of Vaccine Hesitancy

5.5.a.2.a. Vaccine Hesitancy. The "Vaccine Hesitancy" 89 model (see Figure 3) categorizes vaccine hesitancy into 3 C's: Complacency, not perceiving risk or need for vaccine; Convenience, lack of access or cost concerns; and Confidence, lack of trust in the effectiveness and safety of vaccines, the healthcare system, and/or the government. Confidence may be especially salient for Black Veterans and other racial/ethnic minority populations who have experienced medical exploitation and social and economic marginalization.90 The VAI is designed to shift personal vaccine hesitancy towards intrinsic acceptance for receiving the COVID-19 vaccination (see Figure 4). Vaccine hesitancy is an actionable construct because it focuses on vaccine behavior and is influenced by potentially modifiable contextual factors.^{85,91}Vaccine motivation is conceived as an individual behavior influenced by what people think and feel, (i.e., confidence in vaccine benefits and safety, perceived risk to self and others, seeing negative information) and social processes (influence from others, norms, autonomy, trust in providers).³⁰ Vaccine hesitancy and motivation are also dynamically influenced by ever- changing public health and vaccine policies, HCPs' recommendations, new communications and media, all of which exist within socio-cultural. historical and political contexts, and can vary considerably for different Veteran subgroups.⁸⁵ Notably, vaccine hesitancy may be more pronounced with COVID-19 vaccine than other vaccines due to the speed with which it was developed and authorized for emergency use, the pause on the Janssen Johnson & Johnson vaccine for a safety review.⁹² a pervasive internet and social media disinformation campaign, general distrust of the government and healthcare institutions, all compounded by a long history of racial injustice and inequities.

Figure 4. Vaccine Motivation Model⁹⁰

5.5.a.2.b. Risk Communication. In considering how to facilitate a shift from vaccine hesitancy to acceptance, a **risk communication** paradigm is a useful heuristic when there is (1) complex health or risk-related information being communicated; (2) a high level of concern; (3) expert disagreement or high uncertainty; and/or (4) low trust in those responsible for protecting against risk, which describes the context when the COVID-19 vaccine was introduced.¹⁹ An Institute of Medicine report described Risk Communication as a dynamic process responsive to input from several sources, changing concerns of affected populations, modification in scientific risk evidence, and newly identified needs for communication.⁹³ Thus, developing a COVID-19 vaccination acceptance intervention using Risk Communication theory in the context of a pragmatic trial and implementation framework allows for input and feedback from trial stakeholders and adaptation of implementation strategies based on evolving information, and site-specific needs and preferences.⁴⁰ Further, Risk Communication in this intervention will be guided by ethical public health practice recommendations from the CDC, the National Institutes of Health (NIH) Community Engagement Alliance (CEAL), VA Office of Health Equity, and the VA National Center for Health Promotion and Disease Prevention (NCP) and includes:⁹⁴

- **Community engagement** e.g., Veterans, clinics, CBOCs, VAMCs, VISNs, and VACO partners
- **Transparency** through open, honest and comprehensive education about the research and development of vaccines, monitoring of vaccine safety and efficacy, including areas of uncertainty
- Maintaining a **non-judgmental attitude** regarding skepticism and negative attitudes toward vaccines
- Selection of **trusted messengers**, e.g., HCPs and messengers from the same gender, race/ethnicity
- Acknowledgement of indelible impacts of unethical research and racism within healthcare that exploited and/or mistreated Black individuals and individuals from other racial/ethnic minority groups contributing to distrust of COVID-19 vaccine and the healthcare system in general⁹⁵
- Identifying core values for health of individuals and communities in the face of disproportionate negative impacts of the pandemic on women with children, racial/ethnic minority groups, those with mental health disorders, the poor, and other vulnerable populations
- Leveraging of peer influence to promote vaccination, e.g., Veteran opinion leaders and social media and Veteran peer intervention Coaches
- Countering misinformation about COVID-19 vaccines in a collaborative and affirming manner

VA Central IRB

te: December 20, 2023

5.5.a.2.c. Motivational Interviewing (MI). MI is an ideal communication strategy for the VAI. MI is an empathic, non-judgmental evidence-based communication style intended to promote behavioral change consistent with the patient's intrinsic values and goals.⁸⁷ MI has a strong evidence-base across a variety of target behaviors in medical settings (e.g., smoking cessation, treatment engagement, dietary changes)⁹⁶,^{96,97} and has been identified as a promising intervention to address vaccine hesitancy.^{86,98-100} There are several reasons why MI holds promise as an effective COVID-19 vaccine acceptance intervention:

- 1. MI is a **collaborative** approach, which is well-suited for patients who may feel they need to defend their vaccination status or intentions
- 2. **Open questions**, a key strategy in MI, can be used by HCPs to evoke and understand a patient's views about vaccination.
- 3. **Autonomy-supportive statements** (e.g., "only you can decide whether to receive the vaccine") are useful ways of diffusing patient resistance towards vaccination.
- 4. For patients who are ambivalent about vaccination, MI providers can **elicit the patients' personal values** (e.g., to be healthy, concerns about missing work, caring for children or elderly relatives) and how receiving or not receiving the vaccine is consistent with these values.
- 5. Collaborative information-sharing through **Eliciting** the patient's permission to **Provide** information and then **Eliciting** the patient's reaction to the information (Elicit-Provide-Elicit) can be used to share COVID-19 vaccine related information that is personally relevant to the patient.
- 6. MI has a strong evidence-base with **culturally diverse populations**,⁹⁶ including rural populations,¹⁰¹ and has been further adapted for use with racial and ethnic minority populations.¹⁰²⁻¹⁰⁵

5.6Vaccine Acceptance Intervention (VAI) Training Methods

5.6.a Training Health Behavior Coordinators in Vaccine Acceptance. One of this study's operational partners, the VA National Center for Health Promotion and Disease Prevention (NCP) supports MI training of PACT staff throughout VA through a "train-the-trainer model." First, NCP provides in-depth training for all Health Behavior Coordinators (HBCs) that includes content on MI and other patient-centered communication skills, as well as strategies to lead an engaging MI training With PACT staff. Once HBCs have participated in the training, they are then tasked with training PACT staff at their local facility in MI and other patient-centered communication skills. HBCs have trained thousands of PACT providers across the VA health care system in the use of MI and other communication techniques.

During the first 3 months of the study, [name] (Study mPI and SFVAHCS Health Behavior Coordinator) will collaborate with [name] (co-I; CAVHS Health Behavior Coordinator) and [name] (co-I; SFVAHCS Health Behavior Coordinator) to train HBCs based at VAMCs randomized to the VAI condition in VISNs 16 and 21. HBCs will be trained in the Vaccine Acceptance Intervention, which will rely heavily on MI techniques and will also include discussions of vaccine hesitancy and risk communication. The training will closely align with NCP's two-hour MI training for PACT staff so the structure will be familiar to HBCs but will differ from NCP's MI training in that all content will be focused on COVID-19 vaccine acceptance. The estimated time to train HBCs will be approximately 4 hours. The training will review MI training strategies, information regarding COVID-19 vaccines, risk communication and vaccine hesitancy. Following the training, HBCs at intervention sites will be invited to attend a twice-monthly consultation call, to discuss recent advances regarding MI and COVID-vaccine acceptance, to review training strategies and problem-solve any training or intervention issues that may arise.

5.6.b VAI Training for PACT Staff and Coaches. PACT providers (e.g., MDs, NPs, RNs, LVNs, MSAs and other PACT allied health professionals) will be invited to attend a two-hour training in MI, delivered by local HBCs as described above and/or by research team HBCs (i.e., Drs. [name], [name], and [name]). Trainings will be offered to maximize PACT team participation by offering a flexible schedule consisting of either a single two-hour training or two separate one-hour trainings. Trainings will consist of a mix of both didactic instruction and opportunities for practice, including demonstrations and role-plays. Trainings will be offered virtually and in-person via Microsoft Teams. Our partners, NCP and the CDC Vaccinate with Confidence team, have provided relevant materials that will be used to inform innovative provider training, consultation, and VAI delivery. The VAI training manual is included in the appendix.

The VAI training will include MI strategies (e.g., open-ended questions, affirmations, providing empathy), along with key aspects of vaccine hesitancy (e.g, addressing barrier to vaccination) along with risk communication strategies. Our training scripts (see appendix) informed by MI and Whole Health and risk communication strategies follows this sequence:¹⁰⁶

(1) Validate (provider listens with empathy, seeks to validate patients' experience and/or beliefs), (2) Educate (provider asks permission to share information with patient without overstating benefits or minimizing harms), (3) Activate (negotiates SMART goals for vaccination; encourages questions, asks permission to share educational resources and arranges follow-up).

5.6.c Vaccination Scripts. PACT teams and VA staff will be introduced to MI-styled communication scripts designed specifically to increase vaccine acceptance among vaccine hesitant Veterans. These scripts were adapted by NCP, in collaboration with the CDC, to assist VA HCPs in motivating Veterans to accept flu and now COVID-19 vaccination ("Moving to COVID-19 Acceptance"). Scripts will be made into medical chart (CPRS) note templates to facilitate use with patients. Additionally, scripts will be printed on pocket-cards that will include brief communication strategies in a format that allows HCPs to access during appointments with Veterans.

5.6.d Post-Training Consultation. All intervention site PACT and VA staff will be invited to attend a weekly one-hour VISN-wide consultation session (consistent with the Office of Mental Health and Suicide Prevention's national Motivational Interviewing training format where Drs. [name] and [name] serve as MI Consultants). The sessions will be led by site or research team HBCs and will be held at a time that is convenient for clinic staff. Sessions will build upon the skills taught in the initial 2-hour training. Additionally, PACT staff will be invited to share successes and challenges regarding the use of MI vaccine discussions with patients. These consultation sessions could be used as early steps to developing a learning collaborative including PACT staff and the VAI implementation team.

5.6.e. Coach outreach to Veterans. Whole Health Coaches and Peer Specialists will conduct outreach calls to VAI site Veterans. We will work with VISN and site leads to prioritize outreach calls but will consider prioritizing calls to Veterans with upcoming primary care appointments. Coaching sessions will utilize NCP's "Moving to COVID- 19 Vaccine Acceptance" scripts and will be guided by the VAI framework. VAI PACT staff will also be able to place a consult to Coaches and Peer Specialists or add them as co-signers on a clinical note if they have a Veteran who would benefit from further discussion about COVID-19 vaccination.

5.7 Implementation Framework and Training:

5.7.a. Implementation Framework. i-PARiHS⁸⁸ is the implementation framework (Innovation, Recipient, Context, Facilitation) that will be used to adapt and implement the intervention.^{88,107} This framework proposes that implementation facilitation (IF) is the active ingredient, where facilitators activate and support intervention implementation by assessing and responding to the recipients of the intervention within their unique contexts.¹⁰⁸ IF is a multifaceted strategy involving a process of interactive problem-solving and support that occurs in the context of a recognized need for improvement and supportive interpersonal relationships.¹⁰⁹ A number of VA^{107,110} and non-VA^{111,112} studies have shown IF to be an evidence-based strategy for improving implementation of complex evidence-based interventions; this evidence is robust across diverse clinical settings, including under-resourced facilities.¹¹³

The i-PARiHS innovation construct refers to the process of aligning intervention evidence and characteristics with the local practice, priorities, and values. As noted above, the evidence for MI interventions includes a number of health conditions including vaccine hesitancy. The MI intervention derives from our experience developing and testing MI-informed interventions and NCP's experience training VA staff and providers in MI methods and techniques. The recipient construct involves the people who are involved in (primary care staff and HCPs) or expected to be affected by the intervention (Veterans) and includes understanding their motivation, goals, skills, resources, leadership, and organization. The context construct includes understanding inner (local clinic) and outer (health system and community) settings related to implementation. Facilitation is the active ingredient that brings together an understanding of these constructs to enable recipients to adopt, tailor, and apply the innovation to their particular context. To inform future implementation of vaccine acceptance interventions, it will be critical to develop a deep understanding of these implementation constructs and incorporate this understanding into future vaccine acceptance intervention implementation plans. Other discrete implementation strategies that can be used within the context of IF and are relevant to this project include stakeholder discussion/engagement, use of clinician reminders about Veterans eligible for COVID vaccinations with upcoming clinic visits, train-the-trainer where local HBCs are trained to provide the motivational interviewing training to primary care HCPs and clinic staff, action planning, audit and feedback, and creating a learning collaborative for Site Champions and Internal Facilitators.¹⁰⁹ The focus of Aim 3 mid-trial interviews will be on adapting the Vaccine Acceptance Intervention and implementation strategies for this study. Aim 3 end-of-trial interviews will focus on intervention and facilitation strategies to be used in a future roll-outs of vaccine acceptance interventions.

5.7.b. Implementation Facilitation Training. One Internal Facilitator will be identified for each VAMC participating in the intervention arm of the study. Internal Facilitators or research staff who have not completed IF training or who are interested in a refresher will participate in the Implementation Facilitation training. IF is a multifaceted, implementation strategy involving a process of interactive problem-solving and support that occurs in a context of a recognized need for improvement and supportive interpersonal relationships. IF typically bundles an integrated set of activities to support uptake of effective practices, including but not limited to engaging stakeholders, identifying champions, action planning, staff training, academic detailing, problemsolving, providing technical support, audit/feedback and marketing. An increasing volume of literature supports IF as an evidence-based strategy for implementing evidence-based practices (EBPs) and other clinical innovations.

Implementation Facilitation training is supported by Department of Veterans Affairs (VA) Quality Enhancement Research Initiative (QUERI) grants QIS 18-200 and QUE 20-026. While it is targeted to implementation practitioners (clinical and operational staff and/or managers who are conducting implementation efforts), it is also often attended by VA and non-VA researchers and clinical/operational leaders charged with implementing key VA initiatives. Faculty for trainings include [name], [name], [name], [name], and [name]. Together these faculty have decades of experience and substantial expertise in applying and evaluating IF strategies, providing a wealth of experiential knowledge that is shared with trainees during training. At this time, the training is only provided virtually; sessions are split into 4-hour blocks over 4 consecutive days. Internal Facilitators for this study will attend the December 7-10, 2021 training.

5.8. Study Evaluations for Aims 1, 2, and 3

